#### 7.5.4. ANGIOGRAPHIC EXCLUSION CRITERIA

Subjects must not meet any of the following Angiographic Exclusion Criteria. The response for each criterion below must be “No”:

1. Retrograde crossing through target lesion
2. Acute vessel occlusion or acute or sub-acute thrombosis in target lesion
3. Subject has significant stenosis ( $\geq 50\%$  stenosis) or occlusion of ipsilateral inflow iliac artery not successfully treated ( $< 30\%$  residual DS and without complication) prior to PTA of target vessel
4. Angiographic evidence of calcification severe enough that it renders the target lesion non-dilatable and/or has  $\geq 5\text{cm}$  (visual estimate) of circumferential calcification
5. The target lesion shows no dissections after PTA
6. Presence of residual diameter stenosis  $\geq 30\%$  after PTA (based on visual estimate)
7. Non-target limb requiring any vascular treatment at time of index procedure
8. Previously implanted stent in the target vessel

## 8. TREATMENT PLAN

### 8.1. TIME AND EVENTS SCHEDULE

All subjects will receive the assessments at specific time points as listed in **Table 5** below.

#### **Table 5. Time and Events Schedule**

Assessment	Baseline 	Implant Procedure	Pre-Discharge	30-day (-2 days/+14 Days)	6 Month (±30 Days)	12 Month (± 30 Days)	24 Month (± 30 Days)	36 Month (± 30 Days)	Unscheduled 
Informed Consent	X 								
Medical History / Physical Exam	X								
Serum Creatinine	X								
PT/ INR 	X								
Urine pregnancy test if female 	X								
Ankle Brachial Index (ABI)	X		X 	X	X	X	X	X	X
Rutherford Classification	X			X	X	X	X	X	X
Pre-procedural Medications		X							
Angiogram		X							X 
Study Medications		X	X	X	X	X	X	X	X
Duplex Ultrasound (DUS) 				X	X	X			X 
X-ray of Implanted Tacks 						X 			X 
Adverse Event Assessment		X	X	X	X	X	X	X	X
Peripheral Artery Questionnaire (PAQ)	X			X	X	X	X	X	X
EQ-5D-3L	X			X	X	X	X	X	X
Walking Impairment Questionnaire (WIQ)	X			X	X	X	X	X	X

 Assessments may be done up to 30 days before the procedure, with the exception of a pregnancy test

 Consent to be obtained within 30 days prior to enrollment.

 PT/INR to be obtained only if subject is on chronic warfarin therapy.

 Negative urine pregnancy test within 7 days of the Index Procedure is required for women of childbearing potential.

 All scheduled DUS exams should be performed per the protocol established by the core lab. If a DUS is non-diagnostic (per the imaging protocol), the site should make every effort to obtain a repeat exam within the visit window.

 Assessment of Tack Integrity. All required and unscheduled X-ray exams should be performed in accordance with the core lab protocol.

 Unscheduled visit data should be captured for a target limb related adverse event or intervention to target limb. If intervention to the target limb occurs, the data for assessments performed prior to the interventional procedure should be recorded in the eCRF.

 Only required for subjects in whom at least one Tack was placed during the index procedure.

 If clinically indicated or per standard of care.

 Pre-discharge ABI may be assessed up to 72 hours post-index procedure.

NOTE: All imaging of the target limb acquired during scheduled and unscheduled visits (such as Angiogram, DUS or X-Ray) should be submitted to the respective core lab within 3 days of occurrence.

## 8.2. PRE-SCREENING

All subjects presenting to the institution with known superficial femoral and/or proximal popliteal artery disease requiring balloon angioplasty (standard or drug-coated balloon) will be screened for initial eligibility. A trained member of the research team shall perform a preliminary evaluation of the potential subject's medical history and screen for initial eligibility. If during the pre-screening the subject is found to meet one or more exclusion criteria, the subject would be considered a "pre-screen failure". No further action would be taken for pre-screen failure subjects. If determined eligible per initial inclusion criteria, the subject will be approached by qualified research staff and informed about this study through the informed consent process.

## 8.3. OBTAINING INFORMED CONSENT

All sites shall comply with 21 CFR 50, provisions of ICH Good Clinical Practices (GCPs), local IRB/EC policy and all applicable local regulations for obtaining Informed Consent. Written informed consent using the most current IRB/EC-approved informed consent form (ICF) at the time of consent will be obtained for all subjects **prior** to any study-specific screening/baseline tests or procedures are performed. This does not include those procedures or tests that are obtained in the normal course of the subject's non-study related care and prior to undergoing the study procedure, but shall include previously performed tests that may need to be repeated in order to determine eligibility.

All subjects shall possess the ability to understand the information contained in the informed consent form. Subjects will have the study procedures explained in a manner as non-technical as possible, including the risks, benefits and follow-up requirements. If the subject agrees to participate in this study, the subject will personally sign and date the ICF. In the event that a subject possesses the ability to understand the informed consent process and participation in study, but due to physical inability cannot sign the ICF, an impartial witness may sign the ICF on behalf of the subject. Non-English speaking subjects may only be enrolled if they sign an IRB/EC approved and certified translated informed consent form document reflective of his/her spoken language.

Once all required parties have signed the ICF, subjects will receive copies of their signed informed consent documentation.

## 8.4. SCREENING SUCCESS AND FAILURE CRITERIA

Final eligibility of a subject will occur during the Index Procedure. Subjects undergoing an angiographic screen must provide prior informed consent. Every effort will be made to ensure eligibility of the participants prior to enrollment. If no angiographic exclusion criteria are met after pre-enrollment angioplasty, subjects will be considered eligible for enrollment. If at any point prior to or just after pre-enrollment angioplasty, an angiographic exclusion criteria is met, subjects will not be considered eligible for enrollment and will be documented as

“angiographic screen failures”. No further follow-up will be required of these subjects, however; reason for angiographic failure shall be documented by the site into a screening log.

## 9. BASELINE EVALUATION

### 9.1. BASELINE ASSESSMENTS

The following assessments will be performed during baseline evaluation. These examinations and tests will be used both to screen eligible subjects and provide baseline information for those subjects that meet study criteria. All assessments must be completed within the 30 days prior to undergoing the index procedure, except for the urine pregnancy test which must be completed within 7 days of the index procedure with a negative result prior to receiving treatment.

- Demographic information and medical history including risk factors
- Physical examination
  - Height and weight
- Target Limb Resting Ankle Brachial Index (ABI)
- Rutherford Classification
- Serum creatinine ( $\leq 2.5$  mg/dL for inclusion)
- PT & INR (if on chronic warfarin therapy), PLT count
- Urine pregnancy test if female of child-bearing age (within 7 days of procedure)
- Peripheral Artery Questionnaire (PAQ)
- EQ-5D-3L
- Walking Impairment Questionnaire (WIQ)
- Concomitant medications (antiplatelet/anticoagulants)

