### 7.5. SUBJECT SELECTION

#### 7.5.1. INCLUSION CRITERIA

Subjects must meet all the following Inclusion Criteria. The response for each criterion below must be “Yes”:

1. Male or non-pregnant Female  $\geq$  18 years of age at the time of consent
2. Female subjects of childbearing potential must have a negative pregnancy test prior to treatment and must use some form of contraception (abstinence is acceptable) through the duration of the study
3. Target limb requires no additional treatment aside from the target lesion and the iliac artery(ies) during the index procedure
4. Subject has been informed of and understands the nature of the study and provides signed informed consent to participate in the study. If the subject possesses the ability to understand and provide informed consent but due to physical inability, the subject cannot sign the ICF, an impartial witness may sign on behalf of the subject

5. Willing to comply with all required follow-up visits
6. Rutherford Classification 2, 3 or 4
7. Estimated life expectancy >1 year
8. Eligible for standard surgical repair, if necessary
9. Subject is ambulatory (assistive devices such as a cane or walker is acceptable).

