### 7.5.3. EXCLUSION CRITERIA

Subjects must not meet any of the following Exclusion Criteria. The response for each criterion below must be “No”:

1. Rutherford Classification 0, 1, 5 or 6
2. Is pregnant or refuses to use contraception through the duration of the study
3. Previous infrainguinal bypass graft in the target limb
4. Planned amputation on the target limb
5. Systemic infection or Infection within the target limb and/or immunocompromised
6. Endovascular or surgical procedure (not including diagnostic procedures) on the target limb within 30 days prior to or within 30 days after the index procedure
7. Endovascular or surgical procedure (not including diagnostic procedures) on the non-target limb within 14 days prior to the index procedure or planned procedure within 30 days after the index procedure
8. Prior coronary artery bypass graft (CABG) or percutaneous coronary intervention (PCI) procedure within 30 days prior to the index procedure or planned CABG/PCI within 30 days after the index procedure
9. Any other previous or planned surgical or endovascular procedure (not including diagnostic procedures) within 14 days prior to or 30 days post index procedure
10. Planned atherectomy, cryoplasty, stenting or any other treatment (with the exception of a crossing device) of the target lesion other than PTA during the index procedure
11. Known coagulopathy, hypercoagulable state, bleeding diathesis, other blood disorder, or a platelet count less than 80,000/microliter or greater than 500,000/microliter.
12. Known hypersensitivity or allergy to antiplatelet or anticoagulant therapy
13. Myocardial infarction within 30 days prior to enrollment
14. History of stroke within 90 days prior to enrollment
15. Serum creatinine of >2.5 mg/dL
16. Requires treatment of tibial or outflow vessels at the index procedure, which include the P2 and P3 segments of the popliteal artery and the tibioperoneal vessels.
17. Known hypersensitivity or contraindication to nickel-titanium alloy (Nitinol)
18. Participating in another ongoing investigational clinical trial that has not completed its primary endpoint
19. Has other comorbidities that, in the opinion of the investigator, would preclude them from receiving this treatment and/or participating in study-required follow-up assessments
20. Known hypersensitivity or allergy to contrast agents that cannot be medically managed

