#### 10.1.2. BASELINE ANGIOGRAPHIC REQUIREMENTS

Baseline angiographic measurements of the target lesion (visual estimate) shall be captured to determine eligibility and include, but are not limited to the following:

- Target Lesion Location (Prox. SFA, Mid SFA, Distal SFA, Prox. Popliteal [P1])
- Baseline Lesion Length
- Lesion type (Single, Combination or Tandem / De novo or Non-stented restenotic)
- Reference Vessel Diameter (proximal and distal)
- Calcification Severity (None, Mild, Moderate or Severe)
- Baseline Diameter Stenosis (%)
  - Note: The number of subjects with total occlusions (100% occluded target lesion at baseline) will be closely monitored by the sponsor so as not to exceed 20% of subjects enrolled in the study. Once this rate has been reached, sites will be appropriately notified by the sponsor.
- Number of patent (<50% DS) infrapopliteal vessels to the ankle (must have at least one patent vessel that has not been revascularized to qualify for this study)
- Presence of thrombus

Subjects that are eligible for enrollment and present with bilateral stenosis (qualifying lesions in both limbs) may be enrolled under the following conditions:

- The more severe stenosis, per operator discretion, that is intended to be treated with only balloon angioplasty should be considered for enrollment.
- Per operator discretion, the non-target limb lesion can be treated by any appropriate clinical means other than the study device no less than 14 days prior to or 30 days after enrollment (Note: If the PI documents the need for planned intervention on contralateral limb at the time of the index procedure, it would not be considered an adverse event at time of occurrence if treated after enrollment, but this should not be less than 30 days post index procedure).

If subjects that are eligible for enrollment and present with bilateral stenosis are determined by the PI to require intervention during the same procedure, the subject should not be enrolled.

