#### 16.11. OBSERVATIONAL ENDPOINTS

The observational endpoints are listed in **Section 6.2** and are supportive in nature. Descriptive statistics will be calculated and may be provided in labeling if deemed informative for the user. Descriptive statistics for the purposes of labeling are defined as N, mean, standard deviation, median, interquartile range, minimum and maximum for continuous variables and number and percent of observations for categorical variables.

Standard statistical methods will be used and include the Kaplan-Meier product limit method for time to event endpoints and the Wilcoxon signed rank test for changes from baseline for endpoints compared to baseline. Statistical significance will be defined as two-sided  $\square < 0.05$ . Two sided 95% confidence intervals may be calculated for estimates. P-values and 95% confidence intervals are not intended for the labeling.

Safety endpoints will be evaluated in the sample of subjects meeting the ITT definition only. Efficacy endpoints will be evaluated in both the ITT and PP subjects.

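### In staged bilateral subjects the baseline questionnaires can predate treatment of the other leg, so change from baseline can include that procedure (low severity, cheap to close)

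*Combined protocol and SAP*

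**What the plan says.** **Baseline window.** Section 9.1 lists Rutherford class, target-limb resting ABI, PAQ, EQ-5D-3L and WIQ among the baseline assessments and states: "All assessments must be completed within the 30 days prior to undergoing the index procedure". Table 5, footnote 1, agrees: "Assessments may be done up to 30 days before the procedure, with the exception of a pregnancy test".

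**Other leg.** Section 10.1.2 provides for subjects who "present with bilateral stenosis (qualifying lesions in both limbs) may be enrolled under the following conditions". One condition is that the other leg may be treated "no less than 14 days prior to or 30 days after enrollment". Exclusion 7 (section 7.5.3) bars a procedure "on the non-target limb within 14 days prior to the index procedure or planned procedure within 30 days after the index procedure".

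**Ipsilateral iliac.** Inclusion 3 (section 7.5.1) reads "Target limb requires no additional treatment aside from the target lesion and the iliac artery(ies) during the index procedure", so iliac treatment in the index session is allowed.

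**Analysis.** Section 6.2 lists changes from baseline in Rutherford class, ABI, PAQ, EQ-5D-3L and WIQ as observational endpoints. Section 16.11 analyses them with descriptive statistics and "the Wilcoxon signed rank test for changes from baseline for endpoints compared to baseline". It describes them as supportive and allows the descriptive results, but not p-values or confidence intervals, to be considered for labelling.

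No section requires the baseline to be repeated after a non-target-limb procedure, and section 16.11 neither flags nor sets aside subjects who had one.

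**The concern.** Baseline should describe the subject just before the treatment whose effect is being reported. Here the baseline window is longer than the period in which other-leg treatment is barred. The documents tie PAQ, WIQ and EQ-5D-3L to no limb. If they are completed while both legs are symptomatic and one leg is then treated before the index procedure, the later improvement credits both procedures to the index one. With a single arm, no comparator carries the same shift and cancels it.

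At stake is the reading of the reported functional and quality-of-life change, some of which may reach labelling. The date of the other-leg procedure may also be lost. Adverse event reporting starts only at enrollment (section 14), unscheduled visits concern the target limb (section 12.8), and no section expressly asks for this date. If it is not collected prospectively, the affected subjects may be hard to identify later.

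**Working it through.** **1. Day count** (index procedure = day 0)

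| Rule | Source | Allowed |
|---|---|---|
| Baseline questionnaires | 9.1; Table 5 footnote 1 | day -30 to the index procedure |
| Consent | Table 5 footnote 2 | within 30 days before enrollment |
| Non-target-limb procedure | Exclusion 7; 10.1.2 | up to about day -14 |
| Target-limb procedure | Exclusion 6 | none within 30 days before |

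The baseline can precede the other-leg procedure over a span of 30 - 14 = 16 days. The target limb has no such gap, because its 30-day exclusion equals the baseline window.

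**2. Example.** Consent and questionnaires on day -28, other leg treated on day -20, index procedure on day 0.

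- 28 is within 30, so the consent and baseline rules are met.
- 20 is more than 14, so exclusion 7 and section 10.1.2 are met.
- The questionnaires precede the other-leg procedure by 28 - 20 = 8 days.

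The consent limit narrows the sequence but does not prevent it.

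**3. Which endpoints**

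- *PAQ, WIQ, EQ-5D-3L:* exposed, because no limb is specified.
- *Rutherford class:* weaker. The schedule and the section 19 definition name no limb, but the definition of clinically-driven TLR links Rutherford class to target-limb symptoms.
- *ABI:* measured on the target limb, so the window mismatch is not its problem. It has a separate one. Ipsilateral iliac treatment at the index procedure falls between baseline ABI and every follow-up ABI, so the change mixes inflow repair with the target-lesion result.
- *Primary endpoints:* 30-day freedom from MAE and 12-month patency use no questionnaire change. The ABI criterion within clinically-driven TLR is measured from pre-discharge, after any iliac repair.

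**4. Size.** The plan states no figure to reproduce. For a share *s* of subjects affected and a mean effect *d* of the other procedure, the pooled mean change shifts by *s* × *d*. Both inputs below are assumptions.

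| Share *s* | *d* = 10 points | *d* = 20 points |
|---|---|---|
| 0 | 0 | 0 |
| 10% (21 of 210) | 0.10 × 10 = 1 | 0.10 × 20 = 2 |
| 20% (42 of 210) | 0.20 × 10 = 2 | 0.20 × 20 = 4 |

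For ABI with concurrent iliac repair, assuming a share of 0 to 20% and an effect of 0.10 to 0.20, the shift runs from 0 to 0.20 × 0.20 = 0.04.

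**5. Day 14 itself.** Read literally, exclusion 7 excludes a procedure on day -14 and section 10.1.2 allows it. The two should be reconciled.

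**The case against.** The case on the other side is substantial.

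- **The sequence may be rare.** It needs bilateral disease, questionnaires before the other-leg procedure, that procedure in a span of about 16 days, and the index procedure within 30 days of the questionnaires. Section 10.1.2 directs the more severe stenosis to be considered for enrollment, so the less severe leg would have to be treated first. Nothing in the documents supports 10% as a floor. This stands, and it is why the range starts at zero.
- **The endpoints are supportive, and uncontrolled change never isolates the Tack.** It already contains the effect of the angioplasty, with or without a drug-coated balloon. This stands and limits what is at stake. It does not justify adding a procedure on the other leg, which is no part of the index treatment.
- **A repeat soon after the other-leg procedure could record procedural discomfort and lower the baseline.** A repeat placed close to the index procedure largely answers this, because the other-leg procedure is then about 14 days or more in the past.
- **A table excluding anyone with other-leg treatment before the visit would select on later disease course.** Section 10.1.2 allows such treatment from 30 days after enrollment. This also stands, so the exclusion should stop at the index procedure. Later other-leg treatment can still influence the 6- to 36-month changes, and the fix does not remove that.

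A reader might infer that the reported improvement is in fact inflated, or inflated by 1 to 4 points at every visit. The documents do not support either reading. They give no share and no effect, and a constant shift would need an undiminished benefit to 36 months. A reader might also take these to be the trial's only measures of patient benefit, but section 6.2 also lists death, amputation and clinically-driven TLR.

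**Conclusion.** The gap is real and follows from the plan's own windows: a subject can comply with every rule and still have a questionnaire baseline that predates treatment of the other leg. The change in PAQ, WIQ and EQ-5D-3L is then not attributable to the index procedure alone. For Rutherford class the point is weak. For ABI it applies only through concurrent iliac treatment, which is a separate matter.

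The size cannot be computed from the documents. The 0 to 4 points and 0 to 0.04 ABI units rest wholly on assumed shares and effects, and the truth may be close to zero. The expected direction, a larger apparent improvement, assumes that treating the other leg relieves symptoms. Supportive endpoints are affected and neither primary test is. Severity is low, and the change is worth making because it is cheap.

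**What to change.** **Section 9.1 and Table 5 footnote 1.** Add:

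> If a non-target-limb procedure takes place between the baseline questionnaires and the index procedure, PAQ, WIQ and EQ-5D-3L (and target-limb Rutherford class) are repeated as close as practicable before the index procedure, and these values are the baseline. The date of the non-target-limb procedure is recorded.

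**Section 16.11.** Add one supportive table for each change-from-baseline endpoint that excludes subjects with a non-target-limb procedure between the baseline value used and the index procedure. For ABI, also exclude subjects with ipsilateral iliac treatment at the index procedure. Where the repeat was done, the first exclusion removes nobody, so it serves as a backstop for missed repeats.

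**Exclusion 7 and section 10.1.2.** Reconcile the wording for day 14.

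**Cost.** A few repeated questionnaires and Rutherford assessments in staged bilateral subjects, one recorded date, and one extra table per endpoint. The two additions leave who is treated, and when, unchanged.

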## 9.2. STUDY MEDICATIONS

See **Table 6** below for Study Medications

**Table 6. Recommended Study Medications**

Medication	Pre-Procedure	During Procedure	Post-Procedure
Aspirin	Loading dose if required, per institutional standard of care if not on chronic antiplatelet therapy	N/A	81-325 mg/QD indefinitely is recommended
Thienopyridine Class Agent 	Loading dose if required, per institutional standard of care if not on chronic antiplatelet therapy	N/A	75 mg/QD for a minimum of one month recommended 
Heparin	Dosage per institutional standard of care.	Achieve anticoagulation per hospital / institution standard of care 	N/A

 Recommended Thienopyridine class agents include Clopidogrel, Ticlopidine or Prasugrel.

 Recommended daily dose for Clopidogrel. Respective regimen should be prescribed for other thienopyridine agents per Investigator discretion.

 An Activated Clotting Time (ACT) of  $\geq 250s$  is recommended.

